4.2.4 Sub-study analyses

Sub-study endpoints include:

1. The proportion of patients with E. coli detected and the proportion of patients with K. pneumoniae detected within each treatment arm.
2. The proportions of sub-type 0 (phylogroups A or B1) or sub-type 1 (phylogroups B2 or D) among patients with E. coli detected and among patients with K. pneumoniae detected within each treatment arm.
3. The proportions of patients with treatment-susceptible E. coli among patients with E.coli detected and the proportions of patients with treatment-susceptible K.

pneumoniae among patients with K. pneumoniae detected within each treatment arm.

4. The proportion of treatment-resistant E. coli among the patients with E.coli detected and the proportion of treatment-resistant K. pneumoniae among the patients with K. pneumonia detected within each arm.
5. The proportion of colonization with carbapenem resistant Enterobacteriaceae in children after completion of the course of antibiotic therapy for UTI within each treatment arm.
6. Overall biodiversity of the gut microbial community, as measured by culture-independent marker gene sequencing.
7. Overall fraction of gut microbiome community represented by gammaproteobacteria measured by culture-independent marker gene sequencing.
8. Average ecological similarity between microbial communities within and between treatment groups.

The analysis plan for the sub-studies are designed and executed outside of the SCOUT protocol by the Principal Investigators. The analysis for the sub-study is not discussed further in this SAP.

4.2.5 Sub-population analyses

Treatment effects for the primary and secondary endpoints will be estimated as differences between proportions and compared for subpopulations defined by age (defined initially as less than 3 years old, 3 to 6 years old, and 7 to 10 years old), febrile or non-febrile UTI, type of originally prescribed antibiotic, and site. First, proportions will be tabulated as two-sample comparisons and chi-square tests for treatment differences in the endpoints within subgroups will be calculated (*Table 12-*

17 in Section 7.1). Factors where significant differences are observed will be further assessed using logistic regression analysis (*Table 18-23 in Section 7.1*). Goodness of fit test will be reported for model checking. Treatment-by-subpopulation interactions will be tested using likelihood ratio tests. The power of these comparisons is expected to be low for both primary and secondary endpoints. The study is only likely to detect marked differences in treatment effects in these subpopulations. These analyses will use only the per-protocol population with appropriate exclusions (see Section 5.1). Because these analyses are exploratory, significance level at 0.05 will be used.

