differences in microbial carriage and composition between and within subjects over time, we will calculate the UniFrac distance [PMID: 20827291] between all pairs of samples. UniFrac is a measure of the fraction of the evolutionary tree relating all observed taxa that is not overlapping between two samples. To visualize these within- and between-subject differences (beta diversity) and to obtain principal components for subsequent statistical testing, we will perform dimensionality reduction using principal coordinates analysis. To enable tests for shifts in the relative abundance of both broad and specific bacterial taxa with respect to the host factors mentioned above, we will collapse the reference-based OTUs according to taxonomy at the genus and phylum levels using QIIME. This will produce culture-independent fractional observation counts of bacterial taxa in all samples.

We will test for overall differences in microbiome composition between short-course and standard-course antibiotics. To test for associations between individual bacterial taxa and these groups, we will perform non-parametric Mann-Whitney U tests. We will perform a similar test for association of microbiome biodiversity with treatment and between-sample diversity as well as gammaproteobacteria relative abundance.. In all cases the significance of association will be determined after correcting for multiple comparisons using false discovery rate.

Subpopulation Analyses: Treatment effects for the primary and secondary outcome measures will be estimated as differences between proportions and compared for subpopulations defined by age groups, febrile or non-febrile UTI (at original UTI diagnosis), and type of originally prescribed antibiotic. First, proportions will be tabulated as two-sample comparisons and chi-square tests for treatment differences in the outcomes within subgroups will be calculated. Factors where significant differences are observed will be further assessed using logistic regression analysis, assuming that the logistic model fits the data. Goodness of fit test will be reported for model checking. Treatment-by-subpopulation interactions will be tested using likelihood ratio tests. The power of these comparisons is expected to be low for both primary and secondary endpoints. The study is only likely to detect marked differences in treatment effects in these subpopulations.

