Table 10: Comparison of the proportion of children that develop emergent gastrointestinal colonization of antimicrobial resistant E. coli or K.pneumoniae through outcome assessment visit (day 24-30) for per protocol population (Population 4) (Secondary analysis c)

	Arm 1: Standard Course Total= xxx N (%)	Arm 2: Short Course Total= xxx N (%)	p-value for Chi-square test
TOC visit (Day 11-14)			
Outcome assessment visit (Day 24-30)			

Table 11: Comparison of the proportion of children that develop emergent gastrointestinal colonization of antimicrobial resistant E. coli or K.pneumoniae by resistant agent through outcome assessment visit (day 24-30) for per protocol population (Population 4) (Secondary analysis c)

	Arm 1: Standard Course Total= xxx N (%)	Arm 2: Short Course Total= xxx N (%)	p-value for Chi-square test
TOC visit (Day 11-14)			
Emergent Resistance to TMP-SMX			
Emergent Resistance to Amoxicillin-clavulanate			
Emergent Resistance to Ceftazi-dime			
Emergent Resitance to Ampicillin			
Outcome assessment visit (Day 24-30)			
Emergent Resistance to TMP-SMX			
Emergent Resistance to Amoxicillin-clavulanate			
Emergent Resistance to Ceftazi-dime			
Emergent Resitance to Ampicillin			

Table 12. Comparison of the proportion of subjects with symptomatic UTIs prior to or at the TOC visit for subpopulations (Population 2) (Primary endpoint)

	Arm 1: Standard Course Total= xxx N (%)	Arm 2: Short Course Total= xxx N (%)	p-value for Chi-square test
Age Group 2 month – 35 months 3 – 6 years 7-10 years			
Febrile Febrile UTI Non-Febrile UTI			
Antibiotic Type TMP-SMX Amoxicillin-Clavulanate Cefixime Cefdinir Cephalexin			
Site CHOP PITT			

Table 13. Comparison of the proportion of subjects with a recurrent infection at any time after the TOC visit for subpopulations (Population 3) (Secondary endpoint a)

	Arm 1: Standard Course Total= xxx N (%)	Arm 2: Short Course Total= xxx N (%)	p-value for Chi-square test
Age Group 2 month – 35 months 3 – 6 years 7-10 years			
Febrile Febrile UTI Non-Febrile UTI			
Antibiotic Type TMP-SMX Amoxicillin-Clavulanate Cefixime Cefdinir Cephalexin			
Site CHOP PITT			

Table 14. Comparison of the proportion of subjects with asymptomatic bacteriuria at the TOC visit for subpopulation (Population 2) (Secondary endpoint b)

	Arm 1: Standard Course Total= xxx N (%)	Arm 2: Short Course Total= xxx N (%)	p-value for Chi-square test
Age Group 2 month – 35 months 3 – 6 years 7-10 years			
Febrile Febrile UTI Non-Febrile UTI			

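### SAP 4.2.5 picks factors for subgroup modelling by within-subgroup p-values, which do not test whether the treatment effect differs between subgroups; report an interaction test and intervals for every listed factor instead

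*SAP*

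**What the plan says.** The first two subgroup factors in SAP 4.2.5 are these: "age (defined initially as less than 3 years old, 3 to 6 years old, and 7 to 10 years old), febrile or non-febrile UTI". The other two are site and the antibiotic that the treating clinician first chose. The section says treatment effects will be estimated as differences in proportions and compared between subpopulations, for the primary and secondary endpoints. The steps are:

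1. Tables 12–17: "chi-square tests for treatment differences in the endpoints within subgroups will be calculated".
2. Tables 18–23: "Factors where significant differences are observed will be further assessed using logistic regression analysis".
3. A separate sentence: "Treatment-by-subpopulation interactions will be tested using likelihood ratio tests". It does not say whether this covers every factor or only those that passed step 2.

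On the error rate: "Because these analyses are exploratory, significance level at 0.05 will be used". The same section admits that power is low and that only marked differences are likely to be found.

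Protocol 12.4 follows the same order ("chi-square tests for treatment differences in the outcomes within subgroups will be calculated", then logistic regression for factors with significant differences, then likelihood ratio tests of interaction). It does not list site.

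In SAP 7.1, the shells for Tables 12–16 give N (%) per arm and a chi-square p-value, with no column for a difference or an interval. The antibiotic rows are "Antibiotic Type TMP-SMX Amoxicillin-Clavulanate Cefixime Cefdinir Cephalexin". A row for an interaction term appears only in Tables 18–23.

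**The concern.** A test inside one subgroup asks whether treatment has an effect there. The stated aim is to compare effects across subgroups, and that is a question about interaction. The two answers can diverge in both directions: a uniform effect can reach significance in one level by chance of size, and opposite effects in two levels can differ significantly from each other with neither significant alone. The screen therefore selects factors on the wrong quantity.

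The readers' question is whether the short course holds up in, say, febrile or very young children. The planned shells answer it with a low-powered p-value and no interval to set against the 5-point margin. In a non-inferiority trial, a non-significant difference in a small subgroup is not evidence that the short course is acceptable there.

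**Working it through.** **Inputs.** Failure rate 5%, margin 5 points, one-sided alpha 0.05, 326 evaluable per arm (SAP 3.2), so 652 in total; 672 evaluable in Protocol section 5; 1:1 allocation; subgroup alpha 0.05 (SAP 4.2.5), taken as two-sided for a chi-square test. Levels in Table 12: 3 age + 2 fever + 5 antibiotic + 2 site = 12 per endpoint. *Assumed, because the documents do not give them:* subgroup shares (equal and uneven sets were tried) and factors independent of one another. The subgroup analyses use the per-protocol population, whose size is not stated, so 652 and 672 are upper bounds.

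**The plan's own figure.** n per arm = (z₀.₉₅ + z₀.₉₀)² × 2 × 0.05 × 0.95 / 0.05² = (1.645 + 1.282)² × 38 ≈ 8.564 × 38 = 325.4, so 326. For 80% power: (1.645 + 0.842)² × 38 ≈ 6.183 × 38 = 234.9, so 235. Both match SAP 3.2. The SAP gives no error rate for the subgroup screen.

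**How often the screen flags something when nothing is there.** Twelve independent tests would give 1 − 0.95¹² = 46% (11 tests: 43%). The factors divide the same children and the cells are sparse, so the true figure is lower. Simulation at a 5% failure rate, N = 652 or 672, uncorrected chi-square in each level:
- at least one significant level: 33–39% of null trials per endpoint, over the share settings tried;
- by factor: age 13–14%, fever 9–11%, antibiotic 15–22%, site 9–10%;
- over event rates from 2% to 40%: 27–40%.

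**A flag is not an interaction.** With the same effect in both halves of the trial (8% vs 4%, N = 672), the screen flags 56% of trials; the likelihood ratio interaction test is significant in 6%.

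**What would be skipped if only screened-in factors were tested** (20,000 trials each, N = 672, equal-sized levels):

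| Failure rates, short vs standard, by level | Interaction test significant | Of these, no level significant |
|---|---|---|
| 8 vs 5; 2 vs 5 | 49% | 22% |
| 9 vs 4; 3 vs 6 | 62% | 16% |
| 10 vs 5; 5 vs 5 | 21% | 16% |
| 12 vs 5; 5 vs 5 | 31% | 7% |
| 10, 5, 2 vs 5 each (three levels) | 39% | 12% |

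The skipped share is roughly 7–22%.

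**What the alternative costs.** Null rejection rates of the direct likelihood ratio test at a 5% event rate are 5.3% (2 levels), 6.0% (3 levels) and 8.6% (5 levels). For fever, age, antibiotic and site together, treated as independent: 1 − 0.947 × 0.940 × 0.914 × 0.947 = 23%, against a nominal 1 − 0.95⁴ = 19%. Joint simulation gives 23–25% at a 5% event rate and 19–20% at 15%. Requiring both a flag and a significant interaction test in the same factor gives 17–19% and 15%.

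**Sparse cells.** With five equal antibiotic levels, 326 / 5 × 0.05 = 3.3 expected failures per arm per level. The SAP names Fisher's test as the fallback for small expected counts only in the adverse event specifications.

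**The case against.** The strongest reply is that the interaction sentence in SAP 4.2.5 stands alone and carries no restriction. Read that way, every factor gets a likelihood ratio test and nothing is skipped. This stands as a possible reading. Against it, the sentence follows the screening rule and the interaction row exists only in the tables that the screen feeds. The text does not settle the matter.

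A reader might infer that a third of null trials would end in a false subgroup claim. The documents do not support that: a flag leads to further modelling, and a flag followed by a significant interaction test in the same factor occurs in only 17–19% of null trials at a 5% event rate. Nor does dropping the screen reduce false interaction findings; with four unadjusted tests it raises them slightly, to 23–25%.

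It is also fair to say that the SAP calls these analyses exploratory and low-powered, and that Tables 12–17 show every level whether or not it is modelled. Most missed heterogeneity would be due to low power, not to the screen. The figure of about 3 failures per cell assumes equal antibiotic groups, which is unlikely because Protocol 12.4 says amoxicillin-clavulanate was withdrawn as a study antibiotic.

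None of this makes a within-level test an answer to a between-level question.

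**Conclusion.** The point holds, and it is minor. The screening rule in SAP 4.2.5 and Protocol 12.4 selects factors on a test that does not address whether effects differ. Under a global null with 5% failures, about 33–39% of trials show at least one significant level per endpoint; this counts stratum p-values that would be printed in Table 12, not false interaction claims. The loss of roughly 7–22% of significant interactions is conditional on reading the likelihood ratio tests as limited to screened-in factors, and applies to the examples tried. All simulated figures rest on assumed subgroup shares and independent factors. The primary non-inferiority conclusion is not affected.

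**What to change.** In SAP 4.2.5, and in Protocol 12.4 if it is amended:

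- Delete the screening sentence. State that the treatment-by-factor interaction test is reported for age, fever, antibiotic and site, whatever the results within levels.
- In Tables 12–17, replace the within-subgroup p-values with risk differences and 95% intervals, using score or exact methods where cells are sparse. For the primary endpoint, read the intervals against the 5-point margin.
- For antibiotic, use an exact or penalised interaction test, or pool sparse levels by a rule fixed before unblinding, because the likelihood ratio test is liberal there.
- Keep the exploratory label and state that, with four unadjusted tests, about 20–25% of null trials would show at least one p<0.05 per endpoint.
- At the same time, settle the population: the text limits these analyses to per-protocol, while the Table 18 shell names Population 1 (ITT).

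The cost is SAP wording, edits to the table shells and similar programming. No new data are needed. The price in error rate is the small rise in chance interaction findings described above.

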Trimethoprim-sulfamethoxazole (TMP-SMX), cefixime, cefdinir, and cephalexin have been used to treat UTIs in children for decades. These four antibiotics have established safety records for pediatric use and have well described side effect profiles. Antibiotics disturb the normal bowel bacterial flora. During study visits and the follow-up phone call, study participants will be asked to report any potential side effects of the study product, any residual UTI symptoms, and if the child had any hospital or doctor visits for UTI symptoms since their last study contact, and on any possible adverse reactions. All potential serious adverse events (SAEs) or reported side effects will be recorded as study data.

Although the study is using four FDA-approved antibiotics, this study will be conducted under an IND because it will be used to inform the medical community regarding alternative treatment regimens for the antibiotic treatment duration.

Trimethoprim-Sulfamethoxazole (TMP-SMX)

TMP-SMX may cause allergic reactions that range from a mild (skin rash) to severe (Stevens - Johnson syndrome), although severe reactions are extremely rare. Other potential side effects of TMP-SMX include sun sensitivity, recurrent vaginitis, granulocytopenia, and dizziness. Families will be queried about a subject's history of allergies to TMP-SMX. Families will be provided with literature on adverse reactions to TMP-SMX and instructions to call study staff if any evidence of such a reaction occurs.

Cefixime

Cefixime should be avoided by children with a known allergy to cephalosporin type antibiotics. Cefixime is generally well tolerated and side effects are usually transient. Cefixime may cause gastrointestinal issues such as diarrhea, gas, and stomach pain, as well as more severe events such as bloody stools, severe nausea or vomiting or allergic reactions. Families will be queried about a subject's history of allergies to cefixime. Families will be provided with literature on adverse reactions to cefixime and instructions to call study staff if any evidence of such a reaction occurs.

Cefdinir

On occasion cefixime may not be available to the prescribing primary care physician. Under such circumstances it is likely that cefdinir will be prescribed as an alternative agent to cefixime instead. The two antibiotics have therapeutic equivalence.

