5 STUDY DESIGN

The SCOUT Study is a multi-center, centrally randomized, double-blind, placebo-controlled non-inferiority clinical trial. Children will be stratified based on the presence of fever at initial presentation of UTI symptoms and by specific antibiotic therapy prescribed by the original treating clinical provider. Children who have demonstrated clinical improvement five days after starting the originally prescribed antibiotic (afebrile and asymptomatic) will be randomized to standard arm or the short-course arm. Subjects enrolled prior to completion of Day 5 of their originally prescribed antibiotic treatment, will be instructed to complete Day 5 dosing prior to initiating SCOUT study product on Day 6. Subjects enrolled Day 6 should not have started the Day 6 of their originally prescribed antibiotic treatment. The SCOUT study product will consist of trimethoprim-sulfamethoxazole sulfamethoxazole (TMP-SMX), cefixime, cephalexin and the corresponding placebos. If a child initially prescribed cefdinir is enrolled, they will be randomized to either five additional days of cefixime or the cefixime placebo.

About 746 subjects will be enrolled in order to reach 672 evaluable subjects, but the total number that will be ‘enrolled / consented’ may exceed 746 if the study has not enrolled 672 evaluable for the primary endpoint.

Figure 1: Randomization

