Primary Analysis / Efficacy Analysis: The primary analysis will follow Intent-to-Treat (ITT) principles, with subjects analyzed according to randomized treatment assignment. In addition, a “per-protocol” analysis will be performed; the per-protocol analysis would include only subjects who were adherent to their assigned study regimen and completed 80% or more of the prescribed dose. All subjects taking at least one dose of study drug(s) who have been evaluated for treatment success at TOC visit or have failed treatment prior to TOC will be included in the ITT analysis (see the table below). The primary analysis will be a non-inferiority test comparing the number of symptomatic UTIs at the TOC visit between two treatment arms along with the 5% equivalence interval. The confidence interval of the difference in symptomatic UTI rates between the short-course and standard-of-care therapies will be calculated to evaluate whether this difference is less than or equal to the equivalence interval. This will be a one-sided test with $\alpha = 0.05$. Subjects with asymptomatic bacteriuria or who are asymptomatic with a

positive culture including pyuria will NOT be considered treatment failures for the primary outcome measure.

Table 9: SCOUT Study product Dosage Adherence

Antibiotic Drug	Antibiotic Dosage	80% of Expected Doses
Trimethoprim-Sulfamethoxazole (TMP-SMX)	8 mg/kg/day of Trimethoprim in 2 divided doses, Max 160mg BID Trimethoprim	Eight doses
Amoxicillin-Clavulanate*	45 mg/kg/day in 2 divided doses, Max 875 mg Q12H	Eight doses
Cefixime	8 mg/kg/day in 1 dose, Max 400 mg	Four doses
Cephalexin	50mg/kg/day in 3 divided doses	Twelve Doses

*Amoxicillin-clavulanate is no longer included as a study antibiotic, but subjects randomized to this treatment prior to its removal must have taken at least eight doses to be included in the per-protocol analysis.

Secondary Analysis:

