Antibiotic Type TMP-SMX Amoxicillin-Clavulanate Cefixime Cefdinir Cephalexin			
Site CHOP PITT			

Table 15. Comparison of the proportion of subjects with clinical symptoms that may be related to a UTI prior to or at the TOC visit for subpopulation (Population 2) (Secondary endpoint d)

	Arm 1: Standard Course Total= xxx N (%)	Arm 2: Short Course Total= xxx N (%)	p-value for Chi-square test
Age Group 2 month – 35 months 3 – 6 years 7-10 years			
Febrile Febrile UTI Non-Febrile UTI			
Antibiotic Type TMP-SMX Amoxicillin-Clavulanate Cefixime Cefdinir Cephalexin			
Site CHOP PITT			

Table 16. Comparison of the proportion of subjects with positive urine cultures prior to or at the TOC visit for subpopulation (Population 2) (Secondary endpoint e)

	Arm 1: Standard Course Total= xxx N (%)	Arm 2: Short Course Total= xxx N (%)	p-value for Chi-square test
Age Group 2 month – 35 months 3 – 6 years 7-10 years			
Febrile Febrile UTI Non-Febrile UTI			
Antibiotic Type TMP-SMX Amoxicillin-Clavulanate Cefixime Cefdinir Cephalexin			
Site CHOP PITT			

Table 17. Comparison of Risk of emergent colonization with antimicrobial resistant E. coli or K. pneumoniae in Gastrointestinal Tract for Subpopulations (Population 4) (Secondary endpoint c)

	Arm 1: Standard Course Total= xxx N (%)		Arm 2: Short Course Total= xxx N (%)		p- value 1	p- value 2
	TOC visit	Outcome visit	TOC visit	Outcome visit		
Age Group						
2 – 35 months						
3 – 6 years						
7-10 years						
Febrile						
Febrile UTI						
Non-Febrile UTI						
Antibiotic Type						
TMP-SMX						
Amoxicillin- Clavulanate						
Cefixime						
Cefdinir						
Cephalexin						
Site						
CHOP						
PITT						

p-value 1 and p-value 2 will reported from Chi-square test comparing the proportions between sub-populations and treatment arms at TOC visit, and Outcome assessment visit, respectively.

Table 18. Multivariable Logistic Regression Analysis for Treatment failure (Symptomatic UTI at TOC visit) (Population 1) (Primary endpoint)

	Odds ratio	95% CI	p -value
Arm 1 Standard Course(reference)			
Arm 2 Short Course			
Covariates			

Interaction Term			

CI: Confidence Interval

SAS tips: SCALE=NONE in the MODEL statement of the PROC LOGISTIC procedure to generate deviance and Pearson chi-square for goodness of fit test.

Table 19. Multivariable Logistic Regression Analysis for Recurrent Infection at any time after the TOC visit (Population 3) (Secondary endpoint a)

	Odds ratio	95% CI	p -value

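### The subgroup logistic model for treatment failure has no method for sparse antibiotic groups, so some odds ratios may come out infinite or zero, and its named fit check says little

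*SAP*

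**What the plan says.** SAP 4.2.5 works in steps. Treatment effects are first tabulated as differences in proportions by age, fever, originally prescribed antibiotic and site, with a chi-square test in each subgroup. Then: "Factors where significant differences are observed will be further assessed using logistic regression analysis". For interactions: "Treatment-by-subpopulation interactions will be tested using likelihood ratio tests". A goodness-of-fit test is to be reported. The section calls these analyses exploratory and concedes low power.

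The shells in SAP 7.1 supply the detail. Subgroup Tables 12 to 17 list the antibiotic factor as "Antibiotic Type TMP-SMX Amoxicillin-Clavulanate Cefixime Cefdinir Cephalexin", which is five levels. Table 18 (treatment failure) and Tables 19 to 23 (secondary endpoints) have columns for odds ratio, 95% confidence interval and p-value, with blank rows for covariates and an interaction term. The note under Table 18 gives the fit check: "SCALE=NONE in the MODEL statement of the PROC LOGISTIC procedure to generate deviance and Pearson chi-square for goodness of fit test". It does not say how observations are grouped. No penalised, exact or level-pooling method is named.

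Two of the five levels may be small. Protocol 12.4 notes that "Amoxicillin-clavulanate is no longer included as a study antibiotic", without saying how many children had already been randomized on it. Protocol 2.3.1 presents cefdinir as a substitute: "On occasion cefixime may not be available to the prescribing primary care physician". Neither document gives the share of children on any antibiotic.

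Protocol 12.4 makes the logistic step depend on fit; factors are to be "further assessed using logistic regression analysis, assuming that the logistic model fits the data". The SAP drops that condition and only reports the fit test.

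**The concern.** With a failure rate near 5%, a small antibiotic group may have no failures in one arm. In a model with an antibiotic-by-arm term, ordinary maximum likelihood then has no finite estimate for that antibiotic's odds ratio: it runs to infinity or zero and the usual interval is meaningless. The table entry cannot be filled as planned, and the natural response is to merge or drop levels after seeing the data.

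The second issue is the fit check. For a rare binary outcome, the deviance and Pearson statistics do not follow their reference chi-square distribution well. A reader shown a non-significant result could take it as evidence that the model is adequate when it carries little information.

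**Working it through.** **Plan's own figure.** With 5% failure in both arms, a margin of 5 points and one-sided alpha 0.05, the standard formula gives 326 per arm for 90% power and 235 for 80%. Both match SAP 3.2. The plan gives no figure for failures or cell counts in the subgroup models.

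**Expected failures.** The protocol has 672 evaluable children ("About 746 subjects will be enrolled in order to reach 672 evaluable subjects") and the SAP 652. SAP 3.2 assumes 5% failure on standard course and 5% to 9% on short course.

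- 5% v 5%: 672 × 0.05 = 33.6; 652 × 0.05 = 32.6.
- 5% v 9%: 336 × (0.05 + 0.09) = 47.0; 326 × 0.14 = 45.6.

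That is about 33 to 47 failures over 5 × 2 = 10 antibiotic-by-arm cells, and fewer in the per-protocol set.

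**Infinite or zero odds ratios.** Let m be the children per arm on one antibiotic and q = (1 − p)^m the chance of no failures in one cell. With equal rates, the odds ratio for that antibiotic is infinite or zero with probability 2q(1 − q), that is, failures in exactly one arm. Over all antibiotics the chance of at least one is 1 − ∏[1 − 2q(1 − q)].

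Equal shares, 336 per arm, p = 0.05: m = 67.2, q = 0.95^67.2 = 0.0318, 2q(1 − q) = 0.0617, and 1 − (1 − 0.0617)^5 = 0.27. A group with 5% of children has m = 16.8, q = 0.422 and 2q(1 − q) = 0.488 by itself.

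| Assumed antibiotic shares (%) | Any zero-failure cell, 5% v 5% | Infinite or zero odds ratio, 5% v 5% | Infinite or zero odds ratio, 5% v 9% |
|---|---|---|---|
| 20/20/20/20/20 | 28% | 27% | 16% |
| 30/25/20/15/10 | 48% | 45% | 31% |
| 40/25/20/10/5 | 80% | 67% | 59% |
| 35/35/20/5/5 | 90% | 76% | 71% |

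At 5% v 5%, a majority requires one antibiotic at about 7% of children or less with the rest equal, or two at about 10% or less each.

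**Likelihood ratio test.** In simulation (336 per arm, 4,000 null trials per scenario) the statistic was finite in every trial. It rejected 5.7% to 8.8% of the time at a nominal 5%.

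**What a penalised fit gives.** In a single 2×2 table, Firth estimation equals adding 0.5 to each cell. With 17 per arm and 0 v 1 failures, maximum likelihood gives an infinite odds ratio. The penalised estimate is (1.5 × 17.5)/(0.5 × 16.5) = 3.18, with a Wald 95% interval of 0.12 to 83.8. With 34 per arm and 0 v 2 failures it is 5.31 (0.25 to 115). These are finite and very wide.

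**Fit check.** At a 5% rate the ungrouped deviance is −2(33.6 ln 0.05 + 638.4 ln 0.95) = 267. A model with arm and five antibiotics has 672 − 6 = 666 degrees of freedom. A statistic that far below its degrees of freedom will not reject.

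Simulation of a main-effects model (arm, fever, age, five antibiotics, site; assumed mixes) with a strong arm-by-fever effect left out (short course 15% non-febrile v 2% febrile, control 5%):

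- Deviance: rejects in 0% to 0.5% of trials, ungrouped or grouped by full covariate pattern (about 110 patterns).
- Pearson: rejects in about 24% to 31%, ungrouped or grouped. When the model is correct, the grouped version rejects in about 9% at a nominal 5%.
- Likelihood ratio test of the omitted interaction: rejects in about 85%.

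**The case against.** **Most trials.** A reader might infer that the odds ratio fails in most trials. The documents do not support that, because it depends on a mix they do not report; with equal shares the figure is 27%. The removal of amoxicillin-clavulanate and the substitute role of cefdinir make small groups plausible but do not prove them.

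**The significance gate.** Logistic regression is run only for factors with a significant difference. If the gate is a significant within-antibiotic chi-square test, simulation gives both an open gate and an infinite or zero odds ratio in 12% to 14% of trials at 5% v 5%, and in 15% to 39% at 5% v 9%. That stands as an overall frequency. Once the gate has opened under the null, however, the odds ratio is infinite or zero in 69% of trials with equal shares and 84% with the two most skewed mixes. The problem therefore concentrates where the model is used.

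**The interaction test.** A reader might also infer that the planned test breaks down. It does not: it stays finite, is only mildly liberal, and already looks for the omitted interactions. The differences in proportions tabulated first also remain finite. The defect lies in the odds ratios and intervals.

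**The fit check.** It would be too strong to say that it cannot detect misfit. That is essentially true of the deviance but not of Pearson. Grouped on arm-by-antibiotic cells only, Pearson detected a strong omitted antibiotic interaction in 55% to 67% of trials, against 65% to 71% for the likelihood ratio test. The SAP does not define the grouping, so this better case cannot be assumed.

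**Table 18 and pooling.** Table 18 names no antibiotics. The five levels come from Tables 12 to 17 and the subgroup definition in 4.2.5. Originally prescribed antibiotic is also a randomization stratum (Protocol 6.4.1), so replacing it with study product is debatable. Short-course cefdinir children receive cefixime placebo, so cefdinir is the only active drug of the four that they took.

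**Conclusion.** The point holds as an optional improvement to an exploratory analysis. With about 33 to 47 expected failures over five antibiotics, ordinary maximum likelihood gives an infinite or zero within-antibiotic odds ratio in about 27% of trials under equal shares and 67% to 76% under the two most skewed mixes. These figures assume 5% failure in both arms, 336 children per arm and a fitted antibiotic-by-arm model; the shares are assumptions. A higher short-course failure rate lowers them, and the smaller per-protocol set would raise them.

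The named deviance should not be offered as evidence of fit for this endpoint. Pearson misses most strong misfit when ungrouped or grouped by full covariate pattern, and over-rejects in the latter case. The simulated rates depend on the assumed effect and covariate mixes.

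The sparsity figures apply to treatment failure. No event rates are given that would extend them to the endpoints in Tables 19 to 23. The primary non-inferiority test does not use these models.

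**What to change.** Amend SAP 4.2.5 and the Table 18 specifications before unblinding:

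1. Fit Table 18 with the FIRTH option and profile-likelihood intervals. Apply the same to any of Tables 19 to 23 with sparse cells, under a stated rule such as any antibiotic-by-arm cell without events.
2. Keep originally prescribed antibiotic as the factor, but report amoxicillin-clavulanate descriptively and leave it out of the interaction model. Grouping cefdinir with cefixime can be an optional sensitivity analysis.
3. Drop the deviance and Pearson statistics as the fit check and rely on the planned likelihood ratio test of arm interactions. State whether that test is ordinary or penalised.
4. In the same edit, reconcile the analysis population: 4.2.5 restricts these analyses to the per-protocol set, while Table 18 is labelled Population 1.

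The cost is a few lines of SAP text and model options, with no added patients. The penalised test is conservative (about 2% error at a nominal 5% with five groups in simulation), which costs some power where power is already low. The intervals will be wide, but they can be computed and are fixed in advance.
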